2. BACKGROUND AND RATIONALE

Cesarean section (CS) is one of the most frequently performed surgical procedures worldwide, with global rates steadily rising over the past three decades. While CS is a lifesaving intervention when appropriately indicated, it is associated with both short- and long-term complications, particularly those related to uterine scar integrity. Among these, the **cesarean scar defect (CSD)** — also referred to as uterine niche, isthmocoele, or uterine dehiscence — has emerged as a clinically significant sequela that may compromise subsequent reproductive outcomes and maternal health.

A CSD is defined, in accordance with the **European Niche Task Force criteria (Jordan et al., 2019)**, as a triangular anechoic indentation ≥ 2 mm of the anterior uterine wall at the site of the cesarean scar, detected by transvaginal ultrasonography (TVUS). The **residual myometrial thickness (RMT)**, measured

as the minimum thickness of myometrial tissue persisting at the scar site — defined as the distance between the base of the niche (or the scar line when no niche is present) and the outer edge of the uterine serosa, measured at the thinnest point — is considered a reliable surrogate marker for scar healing quality. An **RMT of less than 2.5 mm** is widely accepted as the threshold below which the risk of uterine rupture in subsequent pregnancies is substantially increased.

The technique of uterine closure at the time of cesarean section has long been debated as a modifiable surgical factor influencing scar quality. Two principal closure techniques are currently practiced:

- **Single-layer closure (SLC):** The uterine incision is closed with a single non-locking continuous suture incorporating the full thickness of the myometrium in one pass, including the decidua.
- **Double-layer closure (DLC):** The uterine incision is closed using two successive non-locking continuous extra-mucosal sutures, excluding the decidua: a first layer approximating the inner half of the myometrium, and a second layer burying the first, incorporating the outer half of the myometrium and the uterine serosa.

Despite extensive debate, the literature remains **conflicting and methodologically heterogeneous**. Several randomized controlled trials and meta-analyses have examined these two techniques, yet no definitive consensus has been reached regarding their comparative impact on RMT and CSD formation. Some studies suggest that DLC results in superior RMT and lower CSD rates, while others demonstrate no statistically significant difference, or even suggest potential disadvantages of DLC due to tissue ischemia from excessive suture tension.

Furthermore, the majority of existing studies suffer from significant methodological limitations, including heterogeneous patient populations with prior uterine surgeries, variable follow-up durations, inconsistent ultrasonographic measurement protocols, lack of standardized surgical technique within trial arms, and insufficient sample sizes to detect clinically meaningful differences.

Given the **primary cesarean section** context — where the uterine tissue is native and unaltered by previous scarring — this population provides the ideal setting in which to evaluate the de novo impact of closure technique on scar formation, free from the confounding influence of pre-existing scar pathology.

The present trial is therefore designed to address this evidence gap by conducting a well-powered, prospective, randomized, controlled trial in women

undergoing **primary cesarean section** at CHU Hédi Chaker, Sfax, Tunisia, with standardized surgical technique, blinded ultrasonographic assessment, and rigorous follow-up at 6 weeks and 6 months postoperatively.

3. OBJECTIVES

3.1 Primary Objective

To compare the **residual myometrial thickness (RMT)** at the uterine scar site between single-layer and double-layer hysterorrhaphy techniques, and to compare the **prevalence of cesarean scar defect (CSD)**, at **6 weeks and 6 months** following primary cesarean section, as measured by transvaginal ultrasonography, in order to assess both early scar formation and the stability of the effect over time.

3.2 Secondary Objectives

1. To compare **intraoperative parameters** between groups, including hysterorrhaphy duration, total operative time, visually estimated blood loss (PSTEV), calculated total blood loss (PSTC), number of additional hemostatic sutures, and intraoperative complications.
2. To assess **immediate postoperative outcomes**, including hemoglobin variation (ΔHb), transfusion requirement, early postoperative complications (endometritis, wound infection, parietal hematoma, thromboembolic events, surgical revision), and hospital length of stay.
3. To evaluate **medium-term gynecological symptoms** potentially attributable to CSD at 6 weeks and 6 months, including postmenstrual spotting, prolonged menstruation (> 7 days), dysmenorrhea, chronic pelvic pain, menometrorrhagia, and dyspareunia.
4. To compare **CSD morphological characteristics** between groups, including defect depth, length, width, and estimated volume using the ellipsoid formula.
5. To assess the **adjacent myometrial thickness (AMT)** and the **myometrial ratio ($\text{RM} = \text{RMT}/\text{AMT} \times 100$)** at both evaluation time points.
6. To identify **clinical and surgical predictors** of CSD formation and reduced RMT.
7. To evaluate the **mediating role** of CSD at 6 weeks on RMT at 6 months.

4. STUDY DESIGN

4.1 Design Overview

This is a **prospective, randomized, controlled, parallel-group, single-blind** trial comparing single-layer versus double-layer uterine closure following primary cesarean section. Blinding applies to participants and ultrasonographers performing outcome assessments. The operating surgeon and principal investigator are not blinded due to the nature of the surgical intervention and the necessity of data centralization, respectively.

4.2 Setting

The trial is conducted exclusively at the **Department of Obstetrics and Gynecology, CHU Hédi Chaker, Sfax, Tunisia** — a monocentric study at a tertiary-level university hospital with an established cesarean section program and a dedicated ultrasonography unit.

4.3 Study Timeline

- **Recruitment period:** 01 January 2025 to 31 December 2025 (12 months)
- **Follow-up period per participant:** 6 months (last follow-up visit: 6–7 months after delivery)
- **Primary completion date:** 01 January 2026
- **Study completion date:** 30 April 2026

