6. RECRUITMENT MODALITIES

6.1 Scheduled (Elective) Cesarean Sections

Patients are identified at the preoperative consultation, generally conducted **48 to 72 hours** before the planned intervention. The investigator or a trained team member presents the study, answers questions, and provides the participant information document. Informed consent is obtained on the **morning of the intervention**, after verification of full understanding of the study modalities.

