9. OUTCOME MEASURES

9.1 Primary Outcomes

1. **Residual Myometrial Thickness (RMT)** at the uterine scar site, measured by **transvaginal ultrasonography (TVUS)** at **6–8 weeks** and **6–7 months** postoperatively (millimeters)
2. **Prevalence of Cesarean Scar Defect (CSD)** at **6–8 weeks** and **6–7 months** postoperatively, defined per **European Niche Task Force criteria (Jordan et al., 2019)** as a triangular anechoic indentation **≥ 2 mm** of the anterior uterine wall at the scar site

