10. DATA COLLECTION AND FOLLOW-UP SCHEDULE

Time Point	Assessment
Preoperative	Eligibility verification, informed consent, baseline NFS (CBC), demographics
Intraoperative	Randomization, surgical parameters, hysterorrhaphy duration, operative time, blood loss, complications
Postoperative Day 1	NFS (hemoglobin), vital signs, wound assessment
Discharge	Wound assessment, clinical evaluation, length of stay
6–8 Weeks postpartum	TVUS (RMT, CSD assessment), AMT, RM, clinical examination, standardized symptom questionnaire
6–7 Months postpartum	TVUS (RMT, CSD — PRIMARY ENDPOINT) , AMT, RM, CSD dimensions, volume, standardized symptom questionnaire

Ultrasonographic Examination Protocol

All TVUS examinations are performed:

- By a **dedicated, trained ultrasonographer per center, blinded to group allocation**
- Using **Samsung HS40 ultrasound system with EVN4-9 endovaginal probe (4–9 MHz)**
- With **standardized imaging parameters**

- With the **bladder empty**
- **Preferably in the follicular phase (Day 7–14 of the menstrual cycle)** to optimize defect visualization
- In the **mid-sagittal plane**: depth, length, and RMT measured; width measured in transverse plane
- **RMT measured perpendicular to the serosa at the thinnest point of the scar**

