2. STUDY OVERVIEW

Design: Prospective, randomized, controlled, parallel-group, single-blind trial

Setting: Department of Obstetrics and Gynecology, CHU Hédi Chaker, Sfax, Tunisia (monocentric)

Intervention: Single-layer (SLC) vs. double-layer (DLC) uterine closure after primary cesarean section

Total enrolled: 384 participants (192 per group)

Follow-up: 6–8 weeks and 6–7 months postpartum

Study end date: 30 April 2026

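### The study dates cannot all hold: recruitment to 31 December 2025 puts the last 6–7-month scan at 30 June to 31 July 2026, after both stated completion dates

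*Combined protocol and SAP*

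**What the plan says.** The protocol's section 4.3, Study Timeline, gives four items:

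- Recruitment: "01 January 2025 to 31 December 2025 (12 months".
- Follow-up per participant: "6 months (last follow-up visit: 6–7 months after delivery".
- Primary completion: "01 January 2026".
- Study completion: 30 April 2026. The SAP in the combined document repeats this in its section 2: "Study end date: 30 April 2026".

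The protocol's section 9.1 makes RMT primary "at 6–8 weeks and 6–7 months postoperatively (millimeters", and CSD prevalence is primary at the same two times. Section 3 of the SAP in the combined document lists the same time points. The follow-up schedule (protocol section 10) attaches the label "CSD — PRIMARY ENDPOINT" to the 6–7-month scan only, and section 11 sizes the trial on RMT at 6 months.

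Enrolment and delivery fall on the same day. For scheduled cesareans, "Informed consent is obtained on the morning of the intervention". For all women, allocation is revealed after placental delivery (section 7.2), and section 10 lists randomization as intraoperative.

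**The concern.** The four dates describe one trial and should fit together, but primary completion comes one day after recruitment ends and study completion four months after it. The visit that carries the primary-endpoint label takes place six to seven months after delivery. Nothing in either document mentions early closure of recruitment, a data cut-off, or administrative censoring of late enrollees that would reconcile them.

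At stake is whether the last women enrolled contribute to the analysis on which the trial was sized. Closing on the stated study end date would make their 6–7-month value missing by calendar, for reasons unrelated to their willingness to attend. The missing-data plan (SAP-8 and SAP-10 in the stand-alone SAP; sections 10 and 12 of the SAP in the combined document) is written for dropout and has no category for a visit that is not yet due.

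**Working it through.** **Inputs.** Recruitment 1 January to 31 December 2025 (365 days), last visit at 6–7 months, and completion dates of 1 January and 30 April 2026 (section 4.3). Total 384 women, 192 per group; SD 3.5 mm, difference 1.3 mm, two-sided alpha 0.05, power 80%, 30% loss (section 11). Uniform accrual over the year is my assumption; the documents give no accrual curve.

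**Step 1: the plan's own sample size.** n = 2 × (1.96 + 0.842)² × 3.5² / 1.3² = 113.8, so 114 per group; 114 / 0.70 = 163. Both figures reproduce. The trial enrols 192 per group rather than 163, so it can lose 1 − 114/192 = 40.6% before falling below 114.

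**Step 2: last visits if recruitment runs to 31 December 2025.**

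| Visit of the last woman | Date | Days after 1 Jan 2026 | Days after 30 Apr 2026 |
|---|---|---|---|
| 6 weeks | 11 Feb 2026 | 41 | before it |
| 8 weeks | 25 Feb 2026 | 55 | before it |
| 6 months | 30 Jun 2026 | 180 | 61 |
| 7 months | 31 Jul 2026 | 211 | 92 |

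The stated primary completion date precedes even the last 6–8-week visit. The stated study completion date allows every 6–8-week visit but not every 6–7-month visit. This step needs no assumption about accrual.

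**Step 3: who could not be measured by 30 April 2026.** The last delivery that reaches 6 months by then is 31 October 2025; the last that completes 7 months is 30 September 2025.

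- Window not yet open (November–December deliveries): 61/365 = 16.7%; 0.167 × 384 ≈ 64 women.
- Window not yet closed (October–December deliveries): 92/365 = 25.2%; 0.252 × 384 ≈ 97 women. This is an upper bound, because October deliveries could be scanned in the open part of their window.

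**Step 4: evaluable numbers with the 30% loss applied on top.** Power uses the normal approximation, Φ(1.3 / (3.5 × √(2/n)) − 1.96).

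| Case | Evaluable per group | Total missing | Power |
|---|---|---|---|
| All windows completed | 192 × 0.70 = 134 | 30% | 86.1% |
| Stop on 30 Apr 2026, 6 months reached | 192 × 0.833 × 0.70 = 112 | 41.7% | 79.4% |
| Stop on 30 Apr 2026, 7 months completed | 192 × 0.748 × 0.70 ≈ 101 | 47.6% | 75.0% |

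**Step 5: sensitivity to accrual.** Evaluable n equals 114 when the share not reaching 6 months is 1 − 114/(192 × 0.70) = 15.2%, about 58 women. Slightly sparser enrolment in the last two months would remove the 6-month shortfall; heavier late enrolment would enlarge it.

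**The case against.** The strongest reply is that this may be only a clerical slip. Recruitment may have closed early, or the completion dates may have been entered wrongly; in either case no measurement need be lost. The documents do not define primary completion, and 1 January 2026 might simply mark the end of recruitment. The stand-alone SAP, dated 23 April 2026, says that it was finalized before database lock and unblinding, so on its own account the data were still open then. All of this is fair, and it makes any loss of data conditional. It does not reconcile the dates, since 30 April 2026 still precedes the last 6–7-month visit.

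A reader might also draw four stronger conclusions that the documents do not support:

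- *That late enrollees would have no primary endpoint at all.* RMT and CSD are also primary at 6–8 weeks, and the last such visit ends by 25 February 2026. Only the 6–7-month measures would be lost.
- *That the trial would be analysed on 1 January 2026 with about half the women short of 6 months.* No text says that data collection stops or analysis begins on that date, and a later study completion date is given.
- *That women not yet due would be counted as lost to follow-up.* The plan is silent on them. SAP-10 requires reasons for dropout to be documented and reported, so miscounting is a possibility to guard against, not something the plan prescribes.
- *That the trial becomes seriously underpowered.* Comparing 42–48% missing with the planned 30% ignores the enrolment of 192 rather than 163 per group. Against the 40.6% that 192 can absorb, the excess at 6 months is about one percentage point.

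Missingness by calendar should also be similar in the two arms, given 1:1 allocation in permuted blocks. The cost would be mainly lost precision, not a biased comparison.

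**Conclusion.** Wrong as written. The dates in section 4.3 contradict one another, and the SAP in the combined document repeats the study end date. The conflict is pure calendar arithmetic. It is more than a matter of form, because following the dates literally would leave November–December deliveries without the scan that the schedule labels as the primary endpoint and on which the sample size rests.

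The size of the consequence depends on three conditions: that recruitment ran to 31 December 2025, that follow-up stopped on 30 April 2026, and that accrual was uniform. On those terms the effect on power is negligible if reaching 6 months suffices, and about five points below the 80% target under the full-window bound. The case for correction rests on the impossible timeline, not on power.

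**What to change.** Reconcile the protocol's section 4.3 with section 2 of the SAP in the combined document, in one of two ways:

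1. If recruitment ran to 31 December 2025, set primary and study completion to the close of the last enrolled woman's 6–7-month window, 31 July 2026. State that database lock, unblinding and the primary analysis will not take place before then.
2. If recruitment closed earlier, correct the recruitment end date and derive both completion dates from it.

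In either case, report how many women had reached the 6–7-month visit at data cut-off. Show any woman whose window had not opened or closed by then as not yet due, separately from loss to follow-up, in the flow diagram and the missing-data tables.

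The cost is a correction of dates in two places and, under the first option, a wait of up to about three months (92 days from 30 April to 31 July 2026). No additional women or procedures are needed.

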5. ELIGIBILITY CRITERIA

5.1 Inclusion Criteria

Participants are eligible for enrollment if ALL of the following criteria are met:

Demographic criteria:

1. Female patients aged **18 to 45 years**

Obstetric criteria:

2. **Singleton ongoing pregnancy**
3. Gestational age **> 37 weeks of amenorrhea**, confirmed by **first-trimester ultrasonography**
4. **Non-scarred uterus** (no prior uterine surgery of any kind)

Administrative criteria:

5. Written **informed consent** obtained
6. Patient affiliated with a **social security scheme**
7. Willingness and ability to comply with scheduled **follow-up visits** at 6–8 weeks and 6–7 months postoperatively

5.2 Non-Inclusion Criteria

Participants are not included if ANY of the following criteria are present:

General maternal criteria:

1. **BMI ≥ 35 kg/m²** (morbid obesity)
2. **Pre-gestational diabetes mellitus** (type 1 or type 2)
3. **Autoimmune or chronic systemic diseases**
4. **Hereditary connective tissue disorders**
5. **Constitutional or acquired hemostasis disorders**, or ongoing curative anticoagulation therapy

Obstetric criteria:

6. Suspected or documented **intrauterine infection** (chorioamnionitis)
7. **Abnormal placental insertion** (placenta previa or accreta spectrum)
8. **Retroplacental hematoma**
9. **Multiple gestation**

Uterine criteria:

10. Prior **uterine surgery** or known **uterine malformation**
11. **Documented adenomyosis**

Fetal criteria:

12. **Severe intrauterine growth restriction**
13. **Major known fetal malformation**
14. **Intrauterine fetal death**

5.3 Secondary Exclusion Criteria (Post-Randomization)

Participants are secondarily excluded if the following events occur:

During the intervention:

1. Intraoperative discovery of an **undiagnosed uterine anomaly**
2. Necessity of a **corporeal (vertical) hysterotomy**

3. **Major intraoperative hemorrhage** requiring non-standardized hemostatic procedures

During follow-up:

4. **Loss to follow-up**
5. **Withdrawal of consent**
6. **Occurrence of a new pregnancy before the 6-month evaluation**

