STATISTICAL ANALYSIS PLAN

Official Title:

Single-Layer Versus Double-Layer Uterine Closure After Primary Cesarean Section: Impact on Residual Myometrial Thickness and Cesarean Scar Defect Formation — A Prospective Randomized Controlled Trial

NCT Number: Pending

Protocol ID: 31/26

Document Date: April 23, 2026

Important Note: This Statistical Analysis Plan was finalized prior to database lock and unblinding. Any deviations from this pre-specified plan will be documented and justified in the final statistical report.

**Institution: Department of Obstetrics and Gynecology
Hedi Chaker University Hospital Sfax, Tunisia**

**Principal Investigator: [name], MD
Department of Obstetrics and Gynecology
Hedi Chaker University Hospital, Sfax, Tunisia
Email: [contact]**

**Supervisors: [name]
[name]
Department of Obstetrics and Gynecology**

Ethics Committee Approval: Ethics Committee of the Faculty of Medicine of Sfax, Tunisia

Approval Number: 31/26

STATISTICAL ANALYSIS PLAN (SAP)

Date of Finalization: April 2026

Responsible Statistician: [[name]]

Principal Investigator: [[name]]

SAP-1. GENERAL PRINCIPLES AND PURPOSE

This Statistical Analysis Plan (SAP) has been **prospectively written and finalized prior to database lock and unblinding**. Its purpose is to pre-specify all planned statistical analyses to minimize the risk of outcome reporting bias and post-hoc analytical decisions. Any deviations from this pre-specified plan will be documented with justification and transparently reported in the final statistical report.

All analyses will be conducted using:

- **SPSS version 26.0** (IBM Corporation) — primary analyses
- **R version 4.3** (R Foundation for Statistical Computing) — complementary and advanced analyses

SAP-2. ANALYSIS POPULATIONS

SAP-2.1 Intent-to-Treat (ITT) Population — PRIMARY

All randomized participants, analyzed according to the **treatment group to which they were allocated**, regardless of the actual treatment received or protocol deviations. This constitutes the **primary analysis population**.

SAP-2.2 Per-Protocol (PP) Population — SENSITIVITY

All randomized participants who:

- Received the allocated intervention as specified in the protocol
- Completed the **6-month follow-up visit** with a valid TVUS measurement
- Had no major protocol deviations affecting outcome assessment

SAP-2.3 Safety Population

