Type of cesarean section	Scheduled vs. Intrapartum	Interaction term
Surgeon category	Senior vs. Resident Year 4–5	Interaction term

Test for interaction: Likelihood ratio test comparing models with and without the interaction term.

All subgroup analyses are exploratory and hypothesis-generating. No correction for multiple comparisons is applied to subgroup analyses; results will not drive primary conclusions.

Results will be presented in **forest plots**.

SAP-8. SENSITIVITY ANALYSES

Analysis	Method
SA-1: Per-Protocol population	Repeat primary analysis in PP population
SA-2: Intraoperative complication exclusion	Exclude participants with major intraoperative events (corporeal hysterotomy, hysterotomy extension > 2 cm)
SA-3: Multiple imputation for missing RMT	MICE — 5 scenarios: observed data, LOCF, best case, worst case, 6-week status carry-forward
SA-4: Inverse Probability Weighting (IPW)	Adjust for informative loss to follow-up
SA-5: Binary threshold analysis	Proportion with RMT < 2.5 mm and RMT < 3.0 mm; Chi-square test
SA-6: Complete case analysis	For comparison with imputed results

SAP-9. MULTIPLICITY AND TYPE I ERROR CONTROL

- **Primary outcomes:** $\alpha = 0.05$, two-sided, for each co-primary endpoint (RMT and CSD prevalence at 6 weeks and 6 months)
- **Secondary outcomes:** Exploratory; **Holm-Bonferroni correction** applied to control family-wise error rate
- **Unmeasured confounders:** **E-value** calculated to quantify the minimum strength of an unmeasured confounder needed to explain away observed associations

SAP-10. MISSING DATA STRATEGY

Data Type	Strategy
Primary outcome (RMT at 6 months)	Five imputation scenarios (MICE)
Secondary continuous outcomes	Complete case + sensitivity with imputation if > 10% missing
Binary outcomes	Complete case analysis

Symptom questionnaires	Linear mixed model (full information maximum likelihood)
------------------------	--

Missing data mechanism assessed by **Little's MCAR test**.

Participants lost to follow-up compared to completers on key baseline variables; reasons for dropout documented and reported.

SAP-11. PRESENTATION OF RESULTS

Results reported in accordance with **CONSORT 2010** guidelines:

- **Table 1:** Baseline characteristics (ITT population) — no p-values
- **Figure 1:** CONSORT flow diagram
- **Table 2:** Primary and secondary outcomes with between-group comparisons
- **Table 3:** Subgroup analysis (forest plots)
- **Table 4:** Multivariate analysis results

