7.2 Allocation Timing and Procedure

The group allocation is revealed to the operating surgeon **on the day of the intervention only**, under the following sequential conditions:

1. **Verification of all eligibility criteria**

2. **Signed informed consent obtained**
3. **Fetal delivery and placental delivery completed**
4. **Immediately before performance of hysterorrhaphy**

This sequential allocation procedure ensures that randomization occurs as late as operationally feasible, maximizing allocation concealment and minimizing contamination.

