1. INTRODUCTION AND PURPOSE

This Statistical Analysis Plan (SAP) provides a comprehensive, prospectively defined description of all planned statistical analyses for the SLdl-HYS Trial. It was written and finalized **before database lock and unblinding** to prevent outcome reporting bias and data-driven analytical decisions.

This SAP should be read in conjunction with the Study Protocol (Version 2.0, January 2025). In the event of any discrepancy between this document and the protocol, **this SAP takes precedence** for all analytical decisions. All deviations from this plan will be documented with explicit justification in the final statistical report.

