4. ANALYSIS POPULATIONS

4.1 Intent-to-Treat (ITT) — PRIMARY

All 384 randomized participants, analyzed as allocated regardless of protocol adherence.

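### Protocol 5.3 excludes randomized women after six kinds of event, while both SAPs keep every randomized woman in the primary analysis; the two must be reconciled before database lock

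*Combined protocol and SAP*

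**What the plan says.** Protocol section 5.3 (combined document) states "Participants are secondarily excluded if the following events occur". Three of its six events are intraoperative: a previously undiagnosed uterine anomaly, a corporeal hysterotomy, and major hemorrhage "requiring non-standardized hemostatic procedures". The other three belong to follow-up: "Loss to follow-up", withdrawal of consent, and a new pregnancy before the 6-month assessment.

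The SAPs define the primary population without these exclusions. SAP-2.1 of the standalone SAP takes all randomized participants in their allocated group "regardless of the actual treatment received or protocol deviations". Section 4.1 of the SAP in the combined document reads "All 384 randomized participants, analyzed as allocated regardless of protocol adherence".

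In both SAPs, SA-2 is only a sensitivity analysis; the standalone text is "Exclude participants with major intraoperative events (corporeal hysterotomy, hysterotomy extension > 2 cm". Missing 6-month RMT is handled by imputation scenarios (SA-3) and loss to follow-up by inverse probability weighting (SA-4). The Safety Population is everyone who had the operation.

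Section 1 of the combined document's SAP has a precedence rule that begins "In the event of any discrepancy between this document and the protocol" and gives the SAP priority on analytical decisions. The standalone SAP, dated April 2026, has no such rule. Under Protocol 7.2 the last step before the surgeon learns the allocation is "Immediately before performance of hysterorrhaphy", after delivery of the fetus and placenta.

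**The concern.** A woman cannot be both excluded under 5.3 and analyzed as randomized. Neither SAP refers to 5.3 or says what exclusion means for analysis, so whoever prepares the data set has two incompatible instructions. Protocol 7.3 leaves the principal investigator unblinded, holding both clinical and allocation data.

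The hemorrhage item matters most. Hemorrhage can occur during or after closure, when the unblinded surgeon already knows which technique was assigned, and it may depend on that technique. Section 5.3 defines neither what counts as major nor which procedures are non-standardized. Removing women on this ground could therefore select on an effect of treatment, and the comparison of RMT and CSD would lose part of the protection that randomization gives.

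**Working it through.** **1. The rules side by side**

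- *Corporeal hysterotomy.* Excluded by 5.3. SA-2 removes these women from a set that must therefore contain them. If 5.3 is applied to the analysis, this part of SA-2 has nothing to remove.
- *Loss to follow-up.* Excluded by 5.3. SA-3 and SA-4 exist to represent these same women. If they are gone, the imputation and weighting lose most of their purpose.
- *Major hemorrhage.* Excluded by 5.3. Neither SAP provides any exclusion for it from the primary set.
- *Per-protocol set.* It requires a valid 6-month scan. An ITT set cut down by 5.3 would come close to it, and SA-1 would test little.

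**2. Timing against allocation (Protocol 7.2)**

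The allocation is opened after placental delivery. A corporeal hysterotomy, and usually an anomaly, is known by then, so exclusion that depends on arm is unlikely for these two. Some major hemorrhage also comes before that moment, but some can come during or after closure. Loss to follow-up, withdrawal and new pregnancy all come later.

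**3. The plan's own sample size (Protocol section 11)**

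Inputs: two-sided α 0.05, power 80%, SD 3.5 mm, difference 1.3 mm, 30% loss, 192 enrolled per group.

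- n = 2 × (1.96 + 0.842)² × 3.5² / 1.3² = 113.8, so 114 per group. Reproduced.
- 114 / (1 − 0.30) = 162.9, so 163 per group. Reproduced. Section 11 shows no step from 163 to 192, but nothing here depends on it.

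**4. Power**

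- Observed per group at 30% loss: 192 × 0.70 = 134.4, about 134. Power for 1.3 mm is 86.0%.
- If a further 5%, 10% or 15% of these were excluded, about 128, 121 or 114 remain, with power 84.3%, 82.3% or 80.2%.
- Total attrition can reach 1 − 114/192 = 40.6% before the number falls below 114.

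**5. Possible bias (illustration only; the exclusion rates and RMT deficits are assumed)**

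Suppose there is no true effect and excluded women have mean RMT lower by d than retained women. The spurious difference is then the between-arm difference in exclusion fraction times d. Take d from 1.3 mm to 3.5 mm (one SD). Type I error is computed with 192 per group less the exclusions shown.

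- 2% v 5% excluded: 0.03 × 1.3 = 0.04 mm to 0.03 × 3.5 = 0.11 mm; type I error 5.1% to 6.0%.
- 5% v 10%: 0.05 × 1.3 = 0.07 mm to 0.05 × 3.5 = 0.18 mm; type I error 5.4% to 7.6%.
- 25% v 35%: 0.10 × 1.3 = 0.13 mm to 0.10 × 3.5 = 0.35 mm; type I error 6.1% to 12.9%.

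The first two rows suit an uncommon event such as major hemorrhage. The third would need losses on the scale of the planned 30%, unequal between arms.

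**The case against.** The best defense is that the plan already resolves the conflict. The precedence rule gives the combined document's SAP the last word on analysis, and that SAP keeps all 384. Section 5.3 sits among the eligibility criteria and never says in terms that women leave the analysis; it may only mean that they stop taking part. SA-2, SA-3 and SA-4 all presuppose retention. Much of this stands, and it lowers the practical risk. It does not close the point. The rule does not name 5.3, the later standalone SAP lacks it, and a rule on analytical decisions does not protect a woman whose follow-up was stopped or whose record was removed during conduct. Stopping participation is also an odd meaning for women already lost or withdrawn.

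Some stronger readings are tempting but not supported:

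- *That 5.3 cuts the ITT set from 384 to about 269.* 384 × 0.70 = 268.8 is simply the number expected to have a 6-month RMT at the planned 30% loss, under either reading. CSD, if handled under the binary-outcome rule, is a complete-case analysis anyway.
- *That the worst closures vanish from the safety results.* Both SAPs define the Safety Population as all who had the operation.
- *That any extra hemostatic suture triggers exclusion.* The criterion needs major hemorrhage and non-standardized procedures together; additional sutures are a counted secondary outcome.
- *That the bias has a known direction.* Nothing in the documents establishes one.

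**Conclusion.** The contradiction is real and concerns who is in the primary analysis. On balance the SAP text favors keeping every randomized woman, but it leaves 5.3 standing and unexplained. The risk is bias, chiefly through the hemorrhage item. Its size cannot be stated, because the documents give no exclusion rates by arm. Under the assumed 5% v 10% exclusion, 0.07 to 0.18 mm is about 5% to 13% of the 1.3 mm target and well under one standard error (3.5 × √(2/134) = 0.43 mm). That is modest, but avoidable at little cost. Power is adequate on either reading. The conclusion assumes that some listed hemorrhages occur after the allocation is opened, which 7.2 permits but does not quantify.

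**What to change.** Before database lock, make these changes and carry the same wording into both SAPs:

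- Reword 5.3 so that none of the six events removes a randomized woman from the ITT or safety sets. Record each event as a protocol deviation, an intercurrent event or missing data.
- Limit such exclusions to the per-protocol and SA-2 analyses.
- Restore any woman removed after allocation and keep her ultrasound data where obtained. Use the data of women who withdrew only as far as their consent allows.
- Treat RMT and CSD measured after a new pregnancy has begun as missing, and handle them under the missing-data plan.

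Moving the anomaly and hysterotomy checks ahead of allocation would not help now if recruitment closed on 31 December 2025 as Protocol 4.3 planned.

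The cost is wording in the protocol and both SAPs, plus some data work to trace and restore records. Restoring a woman without a scan adds no observed RMT; it returns her to the denominator, the safety set and the planned imputation. Estimates may shift slightly in either direction.
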